Heuristic Evaluation with experts, Step 2. End-User Usability Evaluation. Step 3. Review by YAB. Note the Youth Advisory Board members will not be self-testing. They will only review the content and function of the app.

Usability Testing. The goal of the usability evaluation is to refine the mLab App User interface. Usability Testing will promote improving the quality of the user's interaction with and perceptions of the mLab App.

Step 1. Heuristic Evaluation. We will conduct a Heuristic Evaluation with five informaticians who will participate as usability experts and must have training in human-computer interaction and have published in the field of informatics.

Procedures.

Heuristic Evaluators will be asked to complete a short demographic survey. Following completion of the survey, the usability experts will be asked to use the Oraquick test and also the mLab App.

The mLab App is mobile app that is accessible using a login name and password. The app will provide HIV prevention information, push notification reminders for testing, step-by-step instructions for using the OraQuick HIV tests, an image upload function to send an image of your OraQuick HIV test to the study team.

Participants will:

- a) be asked to manually enter the Oraquick test results; and
- b) take a picture of the test results for the app to analyze the results; and
- c) receive the app's interpretation of the Oraquick test results.

By using the app, we are asking participants to help test the app's ability to interpret the results of the OraQuick tests. If you test HIV positive by the OraQuick HIV test and/or the mLab app will provide information on how to set up follow-up confirmatory testing within the following 24 hours. All information within the app will be stored on a secured server at Vanderbilt University.

While Morae Software is recording their actions, participants will be asked to use the following use cases while using the app.

First Login

- 1) Taking A Test
 - a. If it's your first time loggingin, it's time for a test, click on the "New Test" tab
 - i. Watch the video
 - ii. Read the instructions and make sure you are clear on how to complete your OraQuick test
(If you need additional help please click the "Help" tab)
 - iii. Do the Oraquick test
 - iv. Click on the start timer
 - v. Do a task you find relaxing for the duration of the timer
 - vi. Read your results and enter what you think they are
 - vii. Get your results on the results page
- 2) Other tasks:

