Step 2. End-User Usability Evaluation. **Study Population.** Our study participants will be young men and transgender women (inclusive of YMSM and YTGW age 18-29 years) who have engaged in recent high-risk sexual behavior with a man. Inclusion criteria. (1) 18-29 years of age (see justification below); (2) assigned male sex at birth of any current gender identification; (3) understand and read English; (4) sexually active and at risk for HIV infection per CDC guidance (e.g., YMSM or YTGW and recent anal sex with men)¹⁰⁷(5) smartphone ownership; and (6) self-report being HIV-negative or unknown status.. Exclusion Criteria. (1) persons who have a known diagnosis of HIV; and (2) persons for whom the investigators determine that participation may be detrimental to the participant or to the study (e.g., severe cognitive deficit).

Justification for Key Inclusion/Exclusion Criteria. The proposed inclusion ages of 18-29 captures the upper range of the greatest increase in new infections,⁵⁴ and the youngest age is the average age when sexual initiation begins^{108, 109} (see Inclusion of Children section). We also carefully considered inclusion of participants who are taking PrEP and will exclude participants who report taking it at baseline. While there is a growing body of literature on poor PrEP adherence,¹¹⁰⁻¹¹² particularly among Blacks and Latinos (NIMHD funding priority) as these are the two racial and ethnic minority groups who are most heavily burdened by HIV,^{4, 6-8, 113} including those on PrEP at baseline would attenuate the intervention effect due to PrEP treatment guidelines, which

include HIV testing at 3-month intervals. We will be collecting data on PrEP use and self-reported adherence to PrEP as part of the trial. Individuals on PrEP at follow-up visits will be encouraged to follow their current treatment protocol with their PrEP provider, including HIV/STI testing requirements and medical visits. We will control for PrEP use at follow-up in all analyses.

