YMSM and YTGW. We will be including BOTH YMSM who have sex with men and YTGW who have sex with men. We believe that targeting of those youth most at-risk of acquiring HIV is the most efficient strategy for implementation in practice. Based on the research to date, barriers to HIV testing for YMSM and YTGW have significant overlap,^{114, 115} suggesting that the mLab App which seeks to overcome these barriers is likely to increase HIV testing uptake in both groups. Nevertheless, we will test potential differences in intervention response by race/ethnicity, sexual and gender minority status (i.e., YMSM vs. YTGW), and co-morbid conditions (i.e., depression and anxiety symptoms, history of trauma) in order to inform future tailoring or targeting of the mLab App.

Settings. This will be a multi-site study in NYC and Chicago. NYC, NY ([name], MPI).¹¹⁶ In 2013, there were 117,618 persons living with HIV in NYC. Of these, 43,940 (over 37%) were infected through male to male sexual contact. Our main recruitment site will be through the Columbia University Medical Center Community Partnership for Health. In addition, we have a number of close community partners in NYC from where we will be recruiting. We work closely the LGBT Center in lower Manhattan and Ali Forney, which provides services for homeless young MSM and TGW and particularly Black and Latino youth. Chicago, IL ([name], MPI). The 2013 rate of HIV infection diagnoses in Chicago (40.4 per 100,000) is approximately 2.5 times higher than the national rate, and the prevalence rate for Chicago (827.9/100,000) is nearly 3 times the national rate. Our main recruitment site will be through The Center for Gender, Sexuality and HIV Prevention at Lurie Children's Hospital within the Division of Adolescent Medicine, directed by [name]. Additionally, we will advertise the study to the entire hospital system in the Chicago area to recruit youth and collaborate with community partners who serve youth.

All of our study activities will be conducted in a private conference room at the Columbia University School of Nursing or at the Lurie Children's Hospital.

Sample. We will recruit 20 youth from both Chicago and NYC to participate in the evaluation of the mLab App interface screens. According to Faulkner,¹¹⁷ 20 users are sufficient to identify 99% of usability problems. Each participant will be given \$40 for participating in the usability evaluation, which is expected to take 60-90 minutes.

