By using the app, we are asking participants to help test the app's ability to interpret the results of the OraQuick tests. If you test HIV positive by the OraQuick HIV test and/or the mLab app will provide information on how to set up follow-up confirmatory testing within the following 24 hours. All information that you provide within the app will be stored on a secured server at Vanderbilt University

We will use Morae software™ and a think-aloud protocol that asks participants to say whatever they are looking at, thinking, doing, and feeling as they go about their task.¹²²⁻¹²⁴ Before we start the task of using the mLab App, we will first explain the think-aloud protocol to the participants and ask them to do the simple practice task of counting the windows in their house/apartment while thinking aloud. The skills demonstration session will be videotaped so that the research team can assess the participant's performance, similar to the one that we created in our work with the HIV OraQuick Test.^{78, 84}

During the think-aloud procedures participants will be asked to complete the following use cases:
mLab Use Cases

First Login

4) Taking A Test

- a. If it's your first time logging in, it's time for a test, click on the "New Test" tab
 - i. Watch the video
 - ii. Read the instructions and make sure you are clear on how to complete your OraQuick test
(If you need additional help please click the "Help" tab)
 - iii. Do the Oraquick test
 - iv. Click on the start timer
 - v. Do a task you find relaxing for the duration of the timer
 - vi. Read your results and enter what you think they are
 - vii. Get your results on the results page

5) Other tasks:

- a. Check for nearby services
- b. Contact us to ask a question
- c. Check history
- d. Look at the HIV facts on the homepage and save the ones you like
- e. Read and watch videos on PEP and PrEP
- f. Check your inbox for messages
- g. Look at your timeline on the homepage for the date of your next test

6) Logout

Second Login

- 8) Check the Testing Timeline on the Homepage to see when your next test should be
- 9) Check history under the Test History tab after getting back the results
- 10) Check for nearby services
- 11) Contact us to ask a question
- 12) Check history under the Test History tab
- 13) If it's not time for a test, you can:
 - a. Look at your timeline on the homepage for the date of your next test
 - b. Check your inbox for messages
- 14) Logout

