Reminder notifications. Participants in the intervention arm will be instructed to use the mLab App and the HIV self-test kit at 3 months, 6 months, 9 months, and 12 months after enrollment. Participants will receive a reminder push notification 2 weeks prior to their scheduled test date and 1 week after their scheduled test date.¹³⁸ In the mLab app, if a participant indicates they have received a preliminary positive HIV test using the home HIV test, participants will be directed to another screen on their smartphone directing them to call the study team or the warm line at the NYP or Lurie clinic (depending on geographic location) to receive follow-up confirmatory testing [and if needed, linkage to care]. Participants will be told that this result does not necessarily indicate that they are HIV positive (see false positive in Protection of Human Subjects), that further follow-up testing is needed, and they should contact the clinic or the study team within 24 hours. The mLab team will return the call within normal business hours. The number and nature of calls from participants to the study team (e.g., related to mLab App use, test interpretation, distress at reactive results) will all be recorded and will be reviewed yearly or at a date determined by the DSMB with our DSMB (see letters of support). We will track linkage to follow-up testing and care. Our DSMB will carefully monitor our study activities and data – see Data Safety and Monitoring Plan. **Sound Retention Efforts.** Participants will be asked after study screening what would be the best way for us to remind them of the appointment (voice phone, text, e-mail). Participant retention during the intervention will be enhanced in several ways. First, participants will be compensated for their time to complete the baseline assessment and completing the follow-up assessments. In addition, during the follow-up survey (6 months), participants will be asked to update their locator information. Using these extensive procedures promotes participant attendance at the follow-up visits, which has been shown to be successful in previous trials.^{139, 140} **We have 4 levels of outcomes:** primary, secondary, intermediate, and program evaluation. The survey items are included in the Qualtrics attachment. The primary outcome for Aim 2 / study trial (Uptake of rapid HIV

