- 5) Window Period for Interpretation of Results: In the mLab App, we have added in 2 points of instruction related to the 20-40 minute window period for the Oraquick results – see Appendix L, slides 7 and 11. Second the images will be time stamped and we will not return algorithm results if the time from reporting in screen 7 and the time to take a picture in screen 11 has been less than 20 minutes or more than 40 minutes.
- 6) Invalid Test Results: If the participant reports an invalid result – the software will send the following message back to the study participant: You reported that your results are invalid. An Invalid test result means that there was a problem running the test, either related to the specimen or to the Test Device. An Invalid test will not be interpreted by the mLab App. Repeat the test with a new Divided Pouch and a new oral fluid. Please contact the study team if you are unable to get a valid test result upon repeat testing. If the participant reports an invalid test then we will turn off the ability for the mLab App to return the algorithm results to the participants. However, invalid images will still be stored in REDCap and reviewed by the study team.
- 7) Imaging Algorithm: The parameter values in the mLab App's image processing algorithm have been validated and selected to primarily optimize sensitivity and specificity. However, it is possible for the mLab App to return both false positives and false negatives. The study team will monitor the images that are sent using the mLab App, and will contact study participants in the event of either: 1) the mLab App returns an incorrect result, and 2) a discrepancy between the participant's manually reported result and the mLab App result.

c. Additional Planned Procedures for Protecting Against/Minimizing Potential Risk/Additional Protections for Children

Procedures in the Event of a Reactive HIV Test

In the event a participant has a reactive HIV test, study team members will counsel the participant regarding the meaning of his result. Specifically, the study team will reiterate with the participant that:

- 1) His result is a preliminary positive and it is likely that he is infected with HIV;
- 2) The preliminary positive result needs to be verified with confirmatory testing;
- 3) He needs to return for the results of his confirmatory testing; and
- 4) Resources for counseling and referral to care are available to him.

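### Aim 1 scripts no reactive, faint-line or invalid result, so hands-on testing of those branches is left to chance and the 99% figure should not be extended to them

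*Combined protocol and SAP*

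**What the plan says.** Aim 1 is to refine the app's interface for home self-testing and for linkage to care.

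- **End users (Aim 1, Step 2).** Twenty users each receive an OraQuick test. The task list is introduced with "During the think-aloud procedures participants will be asked to complete the following use cases". Its result steps are to run the test, enter one's own reading and view the results page. The other tasks cover services, contact, history, facts, PEP/PrEP, inbox and timeline. Eligible users "self-report being HIV-negative or unknown status", and a known diagnosis excludes.
- **Experts (Aim 1, Step 1).** After a short survey, "the usability experts will be asked to use the Oraquick test and also the mLab App", with an equivalent task list. No HIV-status criterion is stated for them.
- **Basis for the number (Aim 1, Step 2, Sample).** The protocol cites a source for the statement that "20 users are sufficient to identify 99% of usability problems".
- **Branches in the app.** For a preliminary positive entered by the user, the Reminder notifications text says "participants will be directed to another screen on their smartphone directing them to call the study team or the warm line"; Recruitment and Informed Consent describes the same step. Protections against Risks, item 6, has a separate path that starts "If the participant reports an invalid result" and ends in a message to repeat the test. Faint lines are described in the Background and Preliminary Data as a reading difficulty and as a reason for having the app.

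**The concern.** The reactive and invalid branches carry the most consequence for a participant, and the reactive branch is the app's own route into linkage to care. A usability test observes performance only on screens that its users open. Under this script nobody is asked to read a reactive, faint or invalid strip and act on what the app shows next.

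The trial does not fill the gap beforehand. Participants must be non-reactive at baseline, and arm 1 then tests with kits taken home. A wording or navigation fault confined to the reactive branch could therefore be met first by someone with a real reactive result. The 99% statement could also be read as assurance about screens that few or none of the 20 users opened.

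**Working it through.** **1. The plan's own figure.** The protocol gives no per-user detection probability, so 99% cannot be reproduced. It can only be back-solved under an assumed model with independent users and a constant probability p of noticing a given problem:

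1 − (1 − p)^20 = 0.99, so p = 1 − 0.01^(1/20) = 0.206.

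Under that model the figure applies only to tasks that all 20 users perform.

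**2. Reactive rate q among end users.** The documents give none for this sample. The values tried are:

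- 1%, 2% and 5%: plain assumptions.
- 2.6% and 11.3%: the Background gives 5% to 20% HIV prevalence in young transgender women, and 49% awareness among infected young men who have sex with men aged 18-24. Applying one group's awareness to the other's prevalence is an assumption. With prevalence π, the undiagnosed share among people without a known diagnosis is π(1 − 0.49)/(1 − 0.49π). For π = 0.05 this is 0.0255/0.9755 = 2.6%; for π = 0.20 it is 0.102/0.902 = 11.3%.
- 25/525 = 4.8% and 40/525 = 7.6%: the 25-40 positive tests expected in the trial (Aim 2, Data Analysis), used only as a rough rate.
- 20%: the upper prevalence unadjusted. This is too high here because known positives are excluded.

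**3. Exposure and detection.** Expected number reaching the branch = 20q. Chance of at least one = 1 − (1 − q)^20. Chance of finding a problem confined to the branch = 1 − (1 − 0.206q)^20.

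| q | Expected of 20 | At least one | Branch problem found |
|---|---|---|---|
| 1% | 0.2 | 18% | 4% |
| 2% | 0.4 | 33% | 8% |
| 2.6% | 0.5 | 41% | 10% |
| 4.8% | 1.0 | 62% | 18% |
| 5% | 1.0 | 64% | 19% |
| 7.6% | 1.5 | 80% | 27% |
| 11.3% | 2.3 | 91% | 37.5% |
| 20% | 4.0 | 99% | 57% |

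If the five experts are counted at the same rates (25 people), the expected number is 0.25 at 1% and 2.8 at 11.3%, and detection is 5% and 44.5%.

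**4. Invalid and faint-line results.** No rate is given for either. At an assumed 1% to 5% each, 0.2 to 1.0 of 20 users would meet one, with an 18% to 64% chance of at least one.

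**5. With every user on the branch.** If all 20 work through a simulated case, exposure is 20 of 20 and the plan's own 99% (p = 0.206) would apply to that branch under the same model.

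**The case against.** A reader might infer that these screens enter the trial untested. The documents do not support that. Ten Youth Advisory Board members review interface, content and function on mock-ups and then try the final app at home. The experts apply a heuristic checklist. Pilot users had already commented on how a positive result is shown. The text does not say which result states these reviews cover, and it excludes none. The workflow attachment and the Appendix L slides are not in the available text. What remains is that none of these activities is said to include the reactive or invalid branch, and none measures whether a target user completes it.

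Four other strong readings also fail:

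- *That staff referral in the session bypasses the app's hand-off.* Step 2 says staff refer a positive participant; it does not say this replaces the app's screen. All users also do the services and contact tasks, although as menu tasks and not as the step after a reactive result.
- *That a faint-line screen is missed.* No such screen is described. What goes unexercised is the reading.
- *That a weak screen leaves participants without a safety net.* In the trial the study team assesses uploaded images, a positive by any of the three readings leads to referral, and staff contact participants when the app is wrong or disagrees with the entered result. These backstops lower the stakes.
- *That the experts' own testing is an error.* Whether an interface inspection needs it is a matter of preference.

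It is also fair that at the upper document-based rate someone would probably see the reactive screen, and that the detection model is not the protocol's.

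**Conclusion.** The point holds as a gap in coverage. Neither the Step 1 nor the Step 2 use cases contain a scripted or simulated reactive, faint-line or invalid result, so hands-on testing of the reactive screen and the invalid message depends on who happens to get which result.

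For reactive rates of 1% to 11%, that means about 0.2 to 2.3 of 20 end users and an 18% to 91% chance of at least one. Under the back-solved model, a problem confined to the reactive branch would be found with probability of about 4% to 37.5%. The rates, the independence of users and p = 0.206 are assumptions. The absence of simulated cases is plain in the text.

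The 99% statement is not shown to be wrong for screens that every user opens; it does not carry over to these branches. The change is worth making for Aim 1's linkage purpose and for participant safety. It affects no randomisation, primary outcome, alpha or power figure in Aim 2.

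**What to change.** 1. Add three clearly labelled mock strips or photographs to the use-case lists in Step 1 and Step 2: clear reactive, faint-line reactive (as a reading task) and invalid.
2. For each, the user reads the strip, enters the result in a test account kept out of the image-review and referral workflow, and follows the app's next screen to the contact or repeat-test step. Score completion per case.
3. Require no photo upload or algorithm reading for the mock cases. Both branches are reached from the user's own entry, and the app withholds its reading for photos outside the 20-40 minute window (Protections against Risks, item 5). The mock cases can be done while the live test develops.
4. Limit the 99% statement in the Sample paragraph to screens that all 20 users open.

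The cost is some added time in a session planned at 60-90 minutes, the setting up of a test account, and labelling clear enough that no one takes a mock result as their own. No extra participants are needed. Replacing the experts' own test with the mock strips is optional.
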